8.1 Main study inclusion criteria

A previous CT scan showing bronchiectasis along with compatible clinical syndrome of cough, sputum production and/or recurrent respiratory tract infections A primary diagnosis of bronchiectasis made by a respiratory physician At the screening visit the individual will have been clinically stable for 4 weeks indicated by the lack of any treatment with antibiotics or corticosteroids for a pulmonary exacerbation in the previous 4 weeks

8.2 Main study exclusion criteria

Inability to give informed consent <18years of age Patients with active tuberculosis Treatment with antibiotics or corticosteroids for a pulmonary exacerbation in the previous 4 weeks Diagnosis of Cystic Fibrosis Previous heart or lung transplant

Cilia substudy criteria will be the same as the main study and in addition:

8.3 Cilia substudy inclusion criteria

Attending a cilia sub-study recruitment site (for example, Ninewells Hospital and Royal Brompton Hospital)

8.4 Cilia substudy exclusion criteria

Smoker – tobacco or vapes An acute upper respiratory tract infection within 6 weeks of visit 1 Known blood clotting disorders Individuals currently taking warfarin or anti-coagulants

8.5 Participant selection and enrolment

Identification of potentially eligible study participants will make use of any or all of the following:

From secondary or tertiary care via contact with patients at specialist respiratory clinics or pulmonary rehabilitation classes. Clinic and class participant lists will be reviewed by the PI (a care team member) or another delegate from the care team and medical records checked to identify suitable patients who will then either be approached and given the Participant Information Sheet (PIS) when they attend clinic or class or will be posted an invite letter and PIS with a reply slip for more information. Contact at clinic or class will be by the PI or delegated person from the care team. Postage of invitation letters with reply slips and PIS will be carried out by the PI or delegate.

From local, national or international databases where patients have given prior consent to be contacted for future research projects e.g. TARDIS, EMBARC, TAYBRIDGE, SHARE, GO-SHARE or related datasets via an invitation letter with reply slip. The local PI will be responsible for recruitment but may delegate to other named individuals within the team. At sites conducting the substudy the PIS will be delivered by the study team (the care team) at visit one to individuals who meet the inclusion criteria.

9.0 Procedures

9.1 Patient procedures

- 1. Informed consent will include consent for biological sampling, long term storage of biological sampling, use of surplus clinical samples in the future and for data linkage.
- 2. Following screening patients will give informed consent to participate and will be asked questions regarding their medical history and medication use.
- 3. Patients will complete the bronchiectasis quality of life questionnaire (Qol-B) and bronchiectasis health questionnaire (BHQ) and at UK sites the bronchiectasis impact measure (BIM).
- 4. Patients will undergo spirometry and Fractional exhaled nitric oxide (FENO) where the test is available

- 5. Spontaneous or induced sputum samples will be collected (patients should ideally provide a sample spontaneously at the study visit, however the priority is to ensure completeness of sampling therefore the following hierarchy is appropriate for sputum sampling- Spontaneous sputum samples: if not possible then induced sputum using hypertonic saline according to local protocol; if unsuccessful then patient may bring a spontaneous sputum to site from home on the day or a different day.
- 6. A blood sample(s) (<50mls) will be collected divided into serum and EDTA anticoagulated blood and Paxgene tubes for RNA studies.
- A buccal swab will be conducted for alpha-1-antitrypsin levels and genotyping. Note that if the patient has previously been tested for alpha-1 antitrypsin levels and this is documented, there is no requirement to perform this further test.
- 8. A stool sample and nasopharyngeal swabs will be collected for microbiome, viral testing and endotyping laboratory investigations described in section 9.2
- 9. For those consenting to the cilia sub-study, nasal brush samples will be collected at baseline and at exacerbation visit for ciliary and epithelial cell investigations described in section 9.2

If individuals have already completed parts of 3-5 as part of the existing ethically approved biobank studies (e.g. BRONCH-UK/TARDIS), or part of their routine clinical care, samples and data may be transferred from the existing biobank. Access to existing samples will be approved by local tissue bank approval processes.

Cilia sub study: At sites in the UK and other sites internationally (where the techniques are available) individuals will be invited to take part in the cilia sub-study. This invitation will be made at the same time as invitation to the main study and will involve additional sampling. Nasal brushing(s) will be taken. This involves removing surface cells from the mucosal lining of the nose with a small cytology brush. Eligible individuals will be invited to take part in the cilia sub study at visit 1 of the main study.

Exacerbation study: Patients will be included in the exacerbation part of the study if they present with an exacerbation during the 3 year study duration which meets the following criteria: At least three of the following: 1) Increased cough 2) Increased

sputum volume or change in sputum consistency 3) Increased sputum purulence 4) Increased breathlessness and/or decrease exercise tolerance 5) Fatigue and/or malaise 6) Haemoptysis, with symptoms lasting for at least 48 hours and requiring treatment with antibiotics. (note that patients may be seen in the first 24 hours of symptoms if appropriate as long as the physician believes that the patient has an exacerbation and that symptoms will last for at least 48 hours).

At this time the individual will have the option to attend the study centre to provide samples or if this is not possible surplus clinical sputum and blood samples will be donated to the study at the patient's convenience during the exacerbation period. If the patient attends their GP, samples can be retrieved through this route or by sending samples from home.

Bronchoscopy study: Individuals in the study undergoing a clinically indicated bronchoscopy at any time during the follow up period will be asked to donate surplus blood, sputum, biopsies, brushings or bronchial alveolar lavage (BAL) fluid.

9.2 Laboratory procedures

Laboratory procedures may include the following:

- 1. Protein proteomic analysis using liquid chromatography–mass spectrometry
- 2. qPCR to evaluate bacterial and viral load
- 3. Assays for inflammatory profiling such as ELISA for cytokine/ chemokine measurement, including neutrophil markers (elastase, resistin, OLF4), alpha 1 anti-trypsin, pH and other candidate markers.
- 4. Microbiome assessment by 16s rRNA amplicon sequencing on the Illumina MiSeq platform for bacteria and ITS sequencing for Fungi
- 5. Assessment of gene expression
- 6. High speed video microscopy to assess and measure ciliary beat frequency, beat pattern and function and electron microscopy (cilia substudy only)
- 7. Fixation and immunohistological staining for protein expression
- 5. Cell culture and subsequent sampling of culture supernatant for cell products
- 6. Challenge of cells with micro-organisms, environmental pollutants and pharmaceutical agents
- 7. Assessment of eosinophil and neutrophil function
- 8. Genotyping (including whole genome sequencing)

All methods will be conducted according to Standard Operating Procedures and Protocols. Anonymised (linked) samples may be sent to collaborators with agreements in place. This includes sharing samples outside the European Union. No BRIDGE Protocol V5 24-03-25 IRAS ID: 228760

identifiable patient details will be provided. Not all of the laboratory procedures will be conducted on all the samples. Procedures conducted at site will depend on local site capabilities and may vary from site to site according to capability.

10.0 Safety assessments

Participants will be asked about adverse events at all visits. We will record adverse events that occur to study participants during a study visit. If any serious adverse events (SAEs) occur they will be reported to the Sponsor based at Ninewells Hospital, Dundee in a timely manner. Refer to section 21.2 for full details on reporting.

The major predictable adverse effects in the study are as follows:

10.1 Induced sputum

The majority of patients will expectorate spontaneous sputum. Some patients may have sputum induction. Bronchospasm is a rare side effect of sputum induction and will be monitored by performing spirometry before or after sputum induction. Patients experiencing symptoms of wheeze, shortness of breath or chest tightness or > 15% reduction in FEV1 from baseline will receive 5mg nebulised salbutamol as a bronchodilator.

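### Section 10.1 asks for spirometry before or after sputum induction, but its rule of a more than 15% FEV1 fall needs a reading on each side

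*Protocol*

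**What the plan says.** Protocol Section 10.0 introduces the subsections on induced sputum and nasal brushing with the words "The major predictable adverse effects in the study are as follows". On induction, Section 10.1 sets out three things:

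- **Who is induced.** "The majority of patients will expectorate spontaneous sputum. Some patients may have sputum induction".
- **Monitoring.** Bronchospasm, which the section calls rare, "will be monitored by performing spirometry before or after sputum induction".
- **Rescue treatment.** Patients with listed respiratory symptoms, or with more than a "15% reduction in FEV1 from baseline will receive" 5 mg of salbutamol by nebuliser. The two conditions are joined by *or*. Baseline is not defined.

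Three other places bear on the point:

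- **Section 9.1, step 4:** "Patients will undergo spirometry and Fractional exhaled nitric oxide (FENO) where the test is available".
- **Section 9.1, step 5:** when the patient cannot produce sputum spontaneously, "if not possible then induced sputum using hypertonic saline according to local protocol".
- **Section 6.0 table:** one row for spirometry, labelled post-bronchodilator, marked at visit 1, at visits 2 to 4 and at the exacerbation visit. Its timing relative to induction is not given.

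**The concern.** The monitoring sentence and the treatment sentence in Section 10.1 do not fit together. The first is met by a single reading on either side of induction. The second acts on a change across induction. Read literally, the monitoring rule does not guarantee the data that the treatment rule uses.

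This is a matter of patient safety, not of inference. The FEV1 criterion adds something to the symptom criterion only when lung function falls and the patient reports no symptoms. That is the case a site would miss if its only reading came before the saline.

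**Working it through.** The plan gives no figure to reproduce. The check sets what the rule needs beside what the text requires.

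**What the rule needs.** With FEV1 measured before (pre) and after (post) induction:

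percent reduction = 100 × (FEV1 pre − FEV1 post) / FEV1 pre

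The rule is met when this exceeds 15, that is, when FEV1 post is below 0.85 × FEV1 pre. Both values are needed.

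**What the text requires.** Section 10.1 requires one reading, before or after. Readings needed (2) minus readings required (1) leaves 1 missing.

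**Whether the rule can be evaluated under each way of complying:**

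| Readings taken | FEV1 rule |
|---|---|
| Before only (for example, the step 4 visit spirometry counted as the Section 10.1 reading) | Cannot be evaluated: no post value |
| After only, with no same-day reading before induction | No valid comparator: no earlier study reading is scheduled at visit 1, and at visits 2 to 4 the last scheduled annual reading is about 12 months old, though an exacerbation visit may add one |
| Step 4 reading before induction, plus a separate reading after | Can be evaluated |

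The symptom rule works in all three rows.

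**Whether another section supplies the missing reading.** Section 9.1 puts spirometry at step 4 and sputum at step 5, with no repeat. The single row in Section 6.0 does not tie spirometry to induction. Neither requires a post-induction reading, so the first row of the table complies with the protocol.

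**Baseline.** The natural reading is the pre-induction value, and the order of steps 4 and 5 normally supplies it. One gap remains. Section 9.1 allows existing data to be used: "If individuals have already completed parts of 3-5 as part of the existing ethically approved biobank studies", or as part of routine care, samples and data may be transferred. Steps 3 to 5 include spirometry. If spirometry is transferred and sputum is newly induced, the reading on file may not be from the day of induction.

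**The case against.** The strongest reply is that the text should be read for its purpose. A reading taken only before induction cannot monitor an effect of induction, and the next sentence acts on a fall, so *and* was very probably meant. If the Section 10.1 reading is additional to the visit spirometry and is taken after induction, there are two readings and the rule works. That reading is sensible. But the text permits it without directing it, and a site with only a pre-induction reading still complies.

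Second, induction follows a local protocol that is not shown and may already call for both readings. This lowers the practical risk, and the document cannot show whether any site omits the second reading. Section 10.1 nevertheless sets its own monitoring rule and its own threshold for an international multi-centre study, and these should work without relying on other documents.

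Third, the consequence is small, and this stands in full. The symptom rule is independent of spirometry. Section 10.0 adds that "Participants will be asked about adverse events at all visits". Induction comes second to spontaneous sputum. Scheduled spirometry is post-bronchodilator, so a patient taken in the listed order has already had a bronchodilator, although the protocol does not say how much protection that gives.

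The baseline point is the weaker part. It needs spirometry to be transferred while sputum is newly induced, which Section 9.1 allows but does not describe.

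**Conclusion.** The point holds, as a minor one. As written, the monitoring rule in Section 10.1 does not secure the data for its FEV1 rule: it falls one reading short per induction at any site that takes only the *before* reading. It is probably a drafting slip. The conclusion about the wording rests on the protocol text alone. The safety consequence also depends on local induction protocols that cannot be seen here.

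The number of inductions is not stated and cannot be derived, so no count of affected visits is possible. How many future inductions a correction would reach is also unsettled. Section 4.0 gives a start in August 2018 and Section 5.0 a duration of 8 years, so the planned end is August 2026, about 16 to 17 months after the version date of 24 March 2025. Section 1.0 also gives a clinical phase of 5 years, which would have ended in August 2023 if it began at study start. Actual progress is not stated.

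No objective, sample size or analysis is affected.

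**What to change.** In Section 10.1, replace *before or after* with *before and after*, and add that baseline means the FEV1 measured before induction at the same visit. The scheduled visit spirometry may serve as that baseline if it is done before induction. The Section 6.0 schedule needs no change.

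The edit is one word and one defining phrase. It needs the approvals in Section 22.0 and can go with the next amendment. The cost to patients and sites is at most one short extra spirometry per induction, on equipment already in use at the visit.

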10.2 Nasal brushing

This procedure has been used routinely for the diagnosis of the inherited condition primary ciliary dyskinesia for several years. This can cause some temporary discomfort but has been showed to be safe and well-tolerated. Occasionally minor nose bleeds can occur following a nasal biopsy. Any nosebleed will be treated appropriately by applying pressure to the nose whilst seated until bleeding ceases.

11.0 Withdrawal procedures

All participants are free to withdraw at any time from the study without giving reasons and without prejudicing further treatment. If they request, all samples and data will be destroyed.

12.0 Data collection and management

12.1 Clinical and demographic data collection

The below are examples of fields already collected by the EMBARC database e.g.- this is not a comprehensive list and other aspects of medical history will be recorded

Age Ethnicity

Gender Height Weight Smoking history Medical history Co-morbidities Number of exacerbations per year Radiological distribution of bronchiectasis on last CT scan Concomitant medications Cause of bronchiectasis and results of diagnostic tests Vaccination history Current physiotherapy techniques Age of diagnosis Previous microbiology and lung function results.

Contact telephone number will be collected for contact to arrange and confirm followup visits and for reminders about exacerbation visits.

12.2 Data Management System

Data management will be conducted in compliance with the Tayside Medical Science Centre (TASC) standard operating procedure on Data Management. The data management system will be the EMBARC registry system, held by the health informatics centre (HIC) University of Dundee as approved by the Sponsor.

The data management system will be based on the protocol and case report form (CRF) for the study and individual requirements of the investigators. The CRF will collect only information that is required to meet the aims of the study and to ensure the eligibility and safety of the participant. The database is managed in line with all applicable principles of medical confidentiality and protection laws. The Data Controller will be the University of Dundee and the Data Custodian will be Health Informatics Centre (HIC).

12.3 Case report form (CRF)

A CRF will be compiled for each participant which will contain subject identification, any correspondence, along with data obtained throughout the study. In addition, details of each visit and any adverse events.

Before this information is shared with any user all identifiable data will be removed. The paper CRFs if used will be stored securely (in a locked room) within the respiratory departments or clinical research centres and will be accessible only by those directly involved within the study. Consent forms will be stored securely and separately from

other study documents. The CRF and consent forms will be stored for a minimum of 10 years and then destroyed.

12.4 Electronic data

Electronic data will be stored as part of the EMBARC project by the Health Informatic Centre (HIC). Individuals registering for this study will also register for the EMBARC study through a single consent form.

Data will be anonymised once all study procedures and follow up are completed.

12.5 Biological samples storage and disposal

All samples will be pseudoanonymised and coded before storage. Samples including blood, culture supernatant and lysed cells will be stored at -80°C. Cells sent for histology will be stored as resin blocks or as slides. Stored samples will be used for any other ethically approved study in the future. Videos and photographs of cells may also be stored. All cellular material will be stored according to the human tissue act under the university license. Ultimately, all cells for which investigation has been completed will be destroyed by incineration.

13.0 Consent

Consent to enter the study will be sought from each participant only after a full explanation has been given to the subject. Signed consent will be obtained from the subject at the start of visit 1 by the local investigator. Where a participant requests to speak with a physician from the study team the consent process will not be completed until the participant has spoken to the physician and had all their questions answered to their satisfaction. Eligible individuals at participating cites will be invited to take part in the cilia sub study at visit 1 of the main study by the local investigator.

For adults who lose capacity their previous wishes will remain legally binding and this will remain valid unless the protocol changes significantly. If this occurs and further consent is required from a participant who has lost capacity, the appropriate person will be asked for their consent. In all cases the CI or delegate will consult with carers and take note of any signs of objection or distress from the participant – the participant will be withdrawn if they raise objection. Where appropriate the participant will be withdrawn from any further clinical intervention and agreement will be sought from a carer to allow data collection.

The informed consent process will be conducted in compliance with TASC SOPs relating to obtaining informed consent from potential participants in clinical research.

14.0 Statistics and data analysis

14.1 Sample size calculation

The sample sizes for each element have had to be chosen subjectively, balancing potential detail against practical limits. As all the sample sizes are greater than 100, they should contain individuals from all subgroups containing more than 10% the population. Study aims one and two classify individuals into groups on the basis of their characteristics, so any realistic power calculations would involve strong assumptions about the distributions and correlations of the measured variables and therefore require data that will be collected during the study. Until that has been collected, the calculations would effectively be guesswork. The investigations for aim three will use as many relevant individuals as are available in the databases and, along with those for aim 4, will be highly dependent on the findings in the earlier stages.

14.2 Proposed analyses

For study aim one, to identify endotypes of bronchiectasis, an unbiased cluster analysis approach will be taken. As the number of practically distinguishable endotypes is unknown, the stability of representations containing different numbers of clusters will be compared, and the importance of the various characteristics to their separation will be investigated.

Study aim 2 will take a similar approach to samples from a smaller number of the patients during exacerbation. As these individuals are a subset of those examined for aim 1, their stable disease endotypes will be considered for inclusion in the cluster analysis. Descriptive statistics will be used to describe the qualities of typical members of each cluster and the differences between clusters.

For aim 3, the patterns identified in the first two parts of the study will be used to classify data from external biobanks and generalized linear models will be used to look for differences in those individuals' responses to treatment and disease trajectories. The classifications will also be applied to the identification of potential participants and samples for the proof of concept studies under aim 4. The analysis of those studies will depend on their particular forms and outcomes but follow generally recognized best practice.

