1.3 Study Design: Observational Cohort study

1.4 Study methods:

Patients with bronchiectasis will be recruited into an observational study, the objectives of which will be to:

Aim 1 will define and validate endotypes of stable bronchiectasis by studying approximately 2500 patients with bronchiectasis. Clinical data (described in the data collection section), sputum microbiome, sputum proteomics, and systemic and sputum inflammatory marker measurement will be incorporated for analysis. A substudy (n=400) will be performed using primary airway epithelial cells. Patients will have brushings of the inferior nasal turbinate with assessment of % ciliation, ciliary beat frequency and pattern by high speed video microscopy before and after culture.

Aim 2 will replicate the phenotyping approach to stable patients with 60 patients during exacerbation. This will identify changes from baseline in microbiota, proteomic and other markers associated with onset of exacerbation and allow classification of clusters of exacerbation.

Aim 3 we will externally validate candidate phenotype/endotypes in registered ethically approved external biobanks and aim to demonstrate that validated markers be linked to potential treatment responses for use in stratified medicine trials.

In total we will recruit approximately 2500 patients for study. These patients will attend one of the participating study centres at least once and undergo sampling along with collecting of clinical data. Patients will be asked to consent for their samples to be linked to data held on an existing pan European bronchiectasis database (the EMBARC registry).

1.5 Nature of outputs and outcomes/results expected:

This study will aim to establish detailed endotypes in bronchiectasis which can guide response to treatment.

2.0 Study background:

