3.2 Secondary Objectives

- 1. To determine molecular endotypes of stable bronchiectasis
- 2. To determine the causes and inflammatory profiles of bronchiectasis exacerbations
- 3. To validate candidate biomarkers of stable and exacerbation endotypes to use in stratified medicine
- 4. To perform in-vivo or in-vitro proof of concept studies using phenotypic data to identify patient populations likely to benefit in future randomized controlled trials

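### Aim 3 promises external validation of endotypes and of biomarkers, but its stated analysis only tests whether BRIDGE-defined classes are associated with outcome

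*Protocol*

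**What the plan says.** Three places in the protocol describe Aim 3.

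- Section 3.2, objective 3 (repeated in 1.2): "To validate candidate biomarkers of stable and exacerbation endotypes to use in stratified medicine".
- Section 1.4, Study methods: "we will externally validate candidate phenotype/endotypes in registered ethically approved external biobanks". The same sentence adds a second intention, about markers: "aim to demonstrate that validated markers be linked to potential treatment responses for use in stratified medicine trials".
- Section 14.2, Proposed analyses: "the patterns identified in the first two parts of the study will be used to classify data from external biobanks". The patients so classified are then compared on treatment response and on disease course by means of generalized linear models.

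Section 14.1 fixes no number for this aim: "The investigations for aim three will use as many relevant individuals as are available in the databases".

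The nearest text to a marker analysis is in the Aim 1 paragraph of 14.2, where "the importance of the various characteristics to their separation will be investigated". That work is done inside BRIDGE, on the data that formed the clusters. Section 14.2 then carries the classifications forward to choose participants and samples for the Aim 4 proof-of-concept studies.

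**The concern.** External validation of an endotype can mean two things: the group exists in other patients, or the label carries information about outcome in other patients. The procedure in 14.2 addresses the second. Applying fixed patterns to new data presupposes the groups, and a later difference in outcome between classes does not establish them. If a marker varies smoothly and outcome follows it, any cut along that marker produces classes with different outcomes.

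The biomarker gap is simpler. Objective 3 is about markers, while the unit of analysis in 14.2 is class membership. No stated step asks how well a marker picks out the members of an endotype.

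The primary objective is endotypes that can guide treatment response. Aim 3 is the one analysis set out in 14.2 that relates endotypes to treatment response; the Aim 4 analyses are left open. A class or marker labelled as validated here would feed the selection of patients for later trials. The point is separate from how clusters are chosen in Aim 1, because clusters that are stable in BRIDGE may still not recur elsewhere.

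**Working it through.** The protocol gives no sample size, effect size or alpha for Aim 3, so there is no figure to reproduce. The check has three parts. Every numerical setting is an assumption that illustrates the logic; none is an estimate for this study.

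**1. Objective against analysis.**

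| Promised (1.4, 3.2) | Stated step in 14.2 |
|---|---|
| Endotypes validated externally | External data assigned to BRIDGE patterns |
| Classes or markers linked to treatment response | Models of response and trajectory |
| Candidate biomarkers validated | None |

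**2. What a significant class difference shows.**

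Settings: three patterns, five markers with unit variance within groups, two centres each 3 SD from the first, external n = 400, nearest-centre assignment, and a one-way test at 5%. The outcome has correlation r with marker 1. The external data are either three real groups or one normal population with the same mean and covariance. There were 2000 runs per setting.

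| External data | r = 0 | r = 0.2 | r = 0.3 | Mean smallest class |
|---|---|---|---|---|
| Three real groups | 5.1% | 85.8% | 99.8% | 30.9% |
| No groups | 5.2% | 78.2% | 99.0% | 30.9% |
| One pattern absent | 5.0% | 87.8% | 99.9% | 3.8% |

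The first three result columns give the share of runs with p < 0.05.

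A formula explains the similarity. Let h be the share of marker 1's variance that lies between the assigned classes. The class model then has R² = r²h, and the F test has noncentrality n·R²/(1 − R²) on 2 and 397 degrees of freedom. Evaluating h numerically in this design gives 0.71 with real groups and 0.56 with none. At r = 0.2:

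- real groups: R² = 0.04 × 0.709 = 0.0284; noncentrality 400 × 0.0284/0.9716 = 11.7; power 87%
- no groups: R² = 0.04 × 0.557 = 0.0223; noncentrality 400 × 0.0223/0.9777 = 9.1; power 77%

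Both agree with the simulation. The test responds to r²h, and h is large whether or not groups exist.

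A different design (20 markers, external n = 500, centres 3-4 SD from the grand mean) gave 87-90% with no groups at r = 0.2 and 100% at r = 0.3, against 96-100% with real groups. A further rerun gave 75-80% against 85-97% at r = 0.2, and 100% in both cases at r = 0.3.

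**3. What separates the two cases.**

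Re-clustering the external data without the BRIDGE labels, and comparing the result with the assigned classes, gives these adjusted Rand indices:

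| Design | Real groups | No groups |
|---|---|---|
| 5 markers, n = 400 | 0.94 | 0.47 |
| 20 markers, n = 500, centres at 3 SD | 0.99 | 0.48 |
| 20 markers, centres at 1.5 SD | 0.81 | 0.45 |
| 20 markers, centres at 1.0 SD | 0.42 | – |

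The contrast is clear for well-separated groups and is lost for weak ones. About 0.45-0.48 arises with no groups at all, so the index needs a single-population reference beside it.

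**Marker performance.** PPV = prev·sens / [prev·sens + (1 − prev)(1 − spec)]. With an assumed 80% sensitivity and 80% specificity:

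- 10% endotype: 0.08/(0.08 + 0.18) = 31%
- 20% endotype: 0.16/(0.16 + 0.16) = 50%

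A marker can therefore look good and still misidentify most of the patients it flags.

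**The case against.** The strongest reply has three parts.

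- **Association is validation of a kind.** Applying a rule derived in BRIDGE to independent patients and testing it against treatment response and trajectory is a recognised and falsifiable exercise, and section 1.4 names the link to treatment response as the purpose. This stands. Requiring discrete clusters to reappear is a stricter question, and a hard rule would reject real but weakly separated groups, as the 1.0 SD row shows.
- **Details belong in a statistical analysis plan.** The assignment rule, agreement measures, cut-offs and thresholds may be specified in a plan that is not at hand, and 14.1 says Aims 3 and 4 depend on earlier findings. This also stands, so their absence is not the finding. The mismatch between objective and analysis does not depend on them: a plan that did only what 14.2 describes would still not evaluate a biomarker.
- **Characteristics are examined.** They are, but only for how they separate clusters within Aim 1.

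A reader might infer more than the protocol supports:

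- That validation will be declared whatever the data show. The protocol does not say so, and the models reject only about 5% of the time when outcome is unrelated to the markers.
- That every external patient must receive a class. The text names no algorithm, and one that leaves patients unassigned would fit it.
- That absence of an endotype could never be seen. A missing pattern left a class of 3.8% instead of 30.9%, although no stated rule reads that signal.

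**Conclusion.** The concern holds as a mismatch between what Aim 3 promises and what 14.2 sets out to do. The stated analysis can support or refute an association between BRIDGE-defined classes and outcome. Alone, it cannot support a claim that the endotypes recur in other populations, and it contains no evaluation of a biomarker.

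Under the assumed settings, a population without groups gave a significant class difference in about 75-90% of runs at r = 0.2 and about 100% at r = 0.3, close to the rates with real groups. These rates depend on the assumed external sample size, number of patterns, separation and marker-outcome correlation. The qualitative conclusion needs only that outcome follows a marker along which the classes are cut.

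Severity is moderate: the mismatch affects how Aim 3 results may be described and what is carried into Aim 4, and it can be corrected cheaply before those results are seen.

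**What to change.** Add to the Aim 3 paragraph of section 14.2:

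1. **Replication.** In external biobanks that hold the clustering variables, also cluster afresh, blind to BRIDGE labels and to outcomes. Report agreement with the BRIDGE-assigned classes, for example the adjusted Rand index with a confidence interval and a single-population reference value. Where a model shows an outcome difference without such agreement, describe it as association of BRIDGE-defined strata with outcome, not as replication of the endotype. Treat agreement as reported evidence, not as a pass/fail rule.
2. **Biomarkers.** Fix each candidate marker and its cut-off in BRIDGE. In the external data, report sensitivity, specificity and AUC with confidence intervals for endotype membership, leaving the marker out of the variables used to classify so that the comparison is not circular. Repeat the generalized linear model on the marker-defined group. If this is not intended, reword objective 3 and section 1.4 to match the class comparison.

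The cost is a few sentences and modest extra analysis of data already to be used. Only biobanks with the same variables can contribute to step 1, and re-clustering has limited power to confirm real but weakly separated groups.
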